### 5.2 Replacement of individual subjects after withdrawal

Not applicable.

### 5.3 Follow-up of subjects withdrawn from treatment

If participants refuse to undergo the 7-day postoperative complications follow-up, they will be excluded from this study.

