## 7 Observation outcomes

### 7.1 Primary outcome

Puncture times of participants for GPS-Lung system and CBCT-guided lung puncture procedures. Puncture times was defined as the number of punctures performed throughout the PLP procedure.

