#### 2.2.2 Second endpoints

Radiation dose, duration of surgery and intraoperative and postoperative complications within 7 days of participants for GPS-Lung system and CBCT-guided lung puncture procedures.

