## Statistical Analysis Plan

- Method of treatment assignment: Participants will be randomly assigned to treatment or control group using a computer-generated random number sequence, with a 1:1 allocation ratio.
- At what point in time subjects are randomized relative to treatments: Participants will be randomized before PLP initiation.

The proposed clinical workflow is present in **Figure 1**

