## Statistical Analysis Plan

### 3.2 Inclusion and exclusion criteria

#### Inclusion criteria

- Participants who require CBCT-guided PLP and meet the clinical indications for the procedure.
- Participants with pre-operation CT images available.
- Participants whose physical condition is suitable for PLP.

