#### Exclusion criteria

- Participants with a history of allergy or serious adverse reactions to iodine contrast media or other related drugs.
- Participants are pregnant or breastfeeding.
- Participants are unwilling or unable to sign informed consent.

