### 3.3 Randomization and binding

Randomization will be performed using a web-based system, employing computer-generated permuted-block sequences with stratification by center. Notably, this centralized, web-based randomization service ensures concealment of trial-group assignments.

A double-blind design will be conducted to ensure that neither participants nor researchers will be aware of group allocation during this study. Participants, researchers, data collectors and outcome assessors will be blinded to group assignment. Statisticians and authors will be also blinded to subgroup allocation during data analysis. Doctors, technicians and trial nurses will be aware of subgroup assignments but will not be involved in data collection or analysis.

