## Statistical Analysis Plan

puncture times). A total of 38 participants received CBCT-guided PLP from retrospective cohort were included from Wuhan Union Hospital. The mean (SD) puncture times of these patients were  $2.3 \pm 2.2$ . We used a 2.5% one-sided significance level with 90% efficacy for sample allocation on a 1:1 basis. The sample size was calculated based on the following formula:

$$n = \frac{2(Z_{\alpha/2} + Z_{\beta/2})^2 * \sigma^2}{\Delta^2}$$

$n$  represents the sample size of each group.  $Z_{\alpha/2}$  represents the critical value of the significance level ( $\alpha$ ), and the  $\alpha=0.025$  in the study.  $Z_{\beta/2}$  represents the critical value of efficacy ( $1 - \beta$ ), and the  $\beta=0.9$  in the study.  $\sigma^2$  represents the within-group variance. In the current,  $\sigma$  was substituted by the standard deviation of puncture times from 38 participants.  $\Delta$  represents the smallest difference between the means of the two groups. In the current, the  $\Delta$  was considered as 1. Therefore, the sample size to be included in this study for each group is 103. We will included 220 participants (each group 110 participants) (Figure 2).

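### Refusing the 7-day follow-up removes a patient from the whole study, so a recorded primary puncture count can be discarded after randomisation because of a secondary outcome

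*SAP*

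**What the plan says.** SAP 5.3, on follow-up of withdrawn subjects, consists of one rule: "If participants refuse to undergo the 7-day postoperative complications follow-up, they will be excluded from this study". It does not say whether refusal is counted before or after randomisation, and the exclusion is from the study as a whole.

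The surrounding text fixes the order of events:

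- **Randomisation.** SAP 3.1: "Participants will be randomized before PLP initiation".
- **Primary outcome.** Protocol 7.1: "Puncture times was defined as the number of punctures performed throughout the PLP procedure".
- **Secondary outcomes.** SAP 2.2.2: "Radiation dose, duration of surgery and intraoperative and postoperative complications within 7 days of participants".
- **Eligibility.** The lists in SAP 3.2 and Protocol section 4 contain no criterion on accepting follow-up. The nearest is about consent only: "Participants are unwilling or unable to sign informed consent".
- **Analysis population.** Protocol section 10 and SAP 5.5 name tests but do not say who is analysed.
- **Missing data.** SAP 5.4 expects none, because most parameters are mandatory surgery-report fields, and it gives no method for the 7-day outcome.
- **Withdrawal.** SAP 5.1 rules out withdrawal once data collection has begun, then excludes people who object to research use of their data, again without a time point. Protocol 12.2 lets participants withdraw whenever they wish.

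**The concern.** Only postoperative complications need the 7-day contact. Puncture count, radiation dose, duration and intraoperative complications are all known when the procedure ends. A rule that drops a refuser from everything lets a later decision by the patient determine who enters the primary comparison, and that decision may depend on how the procedure went.

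Two things are at stake. If refusal is related to the puncture count, the estimated difference can shift even when both arms refuse at the same rate. If that count-related refusal also differs between arms, the type I error moves away from the planned level (SAP 3.4: "We used a 2.5% one-sided significance level with 90% efficacy"). It rises if high-count patients leave the GPS-Lung arm more often and falls if they leave the control arm more often.

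**Working it through.** **1. The plan's own sample size.** Inputs from SAP 3.4: difference 1, SD 2.2, one-sided alpha 0.025, power 90%, 1:1 allocation. For the equal-variance t-test, df = 2n − 2 and the noncentrality is 1 / (2.2 × √(2/n)). Power is 0.8981 at n = 102 and 0.90089 at n = 103, which matches the stated 103 per group and the stated actual power. At the planned 110 per group, power is 91.9%.

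**2. Power lost through exclusions.** Same formula, SD 2.2 in both arms:

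- 14 exclusions split evenly (103 per arm): 90.1%.
- 14 exclusions all in one arm: 90.0%.
- 22 exclusions split evenly (99 per arm): 88.9%.

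The margin above 103 is 14 of 220, or 6.4%. Power is not the main problem.

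**3. Assumed count model for the selection effect.** The documents give neither a refusal rate nor a distribution, so all of this step is assumption. Punctures = 1 + negative binomial. To match the control mean of 2.3 and SD of 2.2, the part above 1 has mean 1.3 and variance 4.84, so size = 1.3² / (4.84 − 1.3) = 0.477. This gives P(1) = 0.534 and P(3 or more) = 0.280. The GPS-Lung arm has mean 1.3 and the same size parameter, which gives SD 0.70.

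**4. Shift in the estimate when refusal is equal in both arms.** True difference 1.00:

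| Who refuses | 10% of them refuse | 20% of them refuse |
|---|---|---|
| Patients with 2 or more punctures | 0.95 | 0.90 |
| Patients with a single puncture | 1.05 | 1.10 |

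**5. Bias with no true effect and refusal in one arm only.** Let a fraction f of patients with 3 or more punctures refuse. From step 3, P(2) = 1 − 0.534 − 0.280 = 0.186. The mean count among patients with 3 or more is (2.3 − 0.534 − 2 × 0.186) / 0.280, about 4.98. The retained mean falls by

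f × 0.280 × (4.98 − 2.3) / (1 − f × 0.280).

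For f = 2%, 5%, 10% and 20% this is 0.02, 0.04, 0.08 and 0.16 punctures. The expected exclusions are 110 × 0.280 × f, about 0.6, 1.5, 3.1 and 6.2 patients.

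**6. One-sided type I error.** Pooled t-test at 0.025, 110 randomised per arm, no true effect, refusal among patients with 3 or more punctures, 100,000 simulated trials per scenario (simulation error at most 0.17 percentage points):

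| GPS-Lung / control refusal | Error |
|---|---|
| 0 / 0 | 2.4% |
| 10% / 10% | 2.4% |
| 20% / 20% | 2.5% |
| 2% / 0 | 2.8% |
| 5% / 0 | 3.3% |
| 10% / 0 | 4.5% |
| 20% / 0 | 7.9% |
| 20% / 10% | 4.6% |
| 0 / 2% | 2.2% |
| 0 / 5% | 1.8% |
| 0 / 10% | 1.3% |
| 0 / 20% | 0.6% |
| 10% / 20% | 1.2% |

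Milder two-arm imbalances give about 3.0% (5% against 2%, GPS-Lung higher) and about 3.3% (10% against 5%).

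The Mann-Whitney test, which SAP 5.5 also allows, behaves the same way (10,000 trials per scenario, simulation error at most 0.55 percentage points). The error is 2.6% with no refusal, 4.3% and 8.5% with GPS-Lung-only refusal at 10% and 20%, and 1.0% and 0.5% with control-only refusal.

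Step 2 uses SD 2.2 in both arms; steps 3 and 4 give the GPS-Lung arm a smaller SD under a true effect. The power figures and the count-model figures answer separate questions and should not be combined.

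**The case against.** The strongest reply is that SAP 5.3 is ambiguous rather than wrong. SAP 5.1 marks withdrawal as not applicable, its exclusion of data objectors reads like a filter at entry, and SAP 5.2 foresees no replacement. On that reading refusers never enter the trial and nothing is lost. This is possible. But follow-up refusal is in neither eligibility list, and SAP 5.3 stands under a heading about subjects already withdrawn from treatment, which points to a later event. Post-randomisation exclusion is therefore permitted by the text, not proven to be intended.

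The second reply is that no figure in the documents supports a bias. That is correct. The error moves only if refusal is both related to the count and unequal between arms. Participants are planned to be blinded, which makes a large imbalance less likely, although "Doctors, technicians and trial nurses will be aware of subgroup assignments". The 7.9% needs 20% refusal among high-count GPS-Lung patients and none in control; modest imbalances give about 3%. In the one-arm cases from 2% to 10% the bias is only 0.02 to 0.08 punctures, against a planned difference of 1.

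These points limit the size of the concern. They do not remove it, because the rule has no stated analytic benefit and nothing elsewhere in the plan puts the excluded patients back.

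**Conclusion.** The concern holds in its conditional form. As written, SAP 5.3 allows a randomised patient with a complete puncture count to be dropped from the primary analysis for declining a secondary assessment, and no analysis set prevents it. The real effect is unknown and may be small. Under the assumed model, equal refusal leaves the error at about 2.5% but can move the estimate by 5% to 10% of the true difference. Unequal refusal among high-count patients moves the error either way, from about 0.6% to 7.9% across the scenarios shown, and about three selective exclusions in the GPS-Lung arm are enough to reach about 4.5%. Power loss is minor. This should be fixed. Confidence is medium, because the intended timing is not stated and every refusal rate is assumed.

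**What to change.** Replace SAP 5.3 with wording such as: *All randomised participants with a recorded procedure are analysed in their assigned group for puncture count, radiation dose, duration and intraoperative complications. Refusal of the 7-day follow-up after randomisation makes only the 7-day postoperative complication outcome missing; events known up to last contact are retained.* If willingness to be followed is meant as an entry condition, list it in SAP 3.2 and Protocol section 4 and apply it before randomisation.

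Reconcile SAP 5.1 with Protocol 12.2 and give the data-objector exclusion a time point, so that it is clear which recorded data may be kept for someone who refuses follow-up, withdraws or objects. Report refusals by arm.

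Two additions are useful but secondary: a best-case/worst-case sensitivity analysis for 7-day complications, and a statement in SAP 5.4 that this outcome may be missing, with its data source named.

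The cost is SAP wording and a reconciling sentence with Protocol 12.2, plus a Protocol section 4 change if the entry-condition route is taken. SAP section 8 requires changes made after ethics approval to be submitted for review. No extra patients or follow-up are needed; the only added analysis is the optional sensitivity analysis.

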### 5.4 Missing data processing

Missing data are not expected, as most parameters are obligatory fields in the PLP surgery reports that will be used in this study.

## Statistical Analysis Plan

### 5.5 Primary and secondary study parameter(s)

For primary outcome, secondary outcomes and baseline comparisons between the two groups, appropriate statistical tests (parametric or non-parametric) will be applied to categorical variables (Chi-squared test/Fisher's exact test) or continuous variables (*t*-test, Mann-Whitney U test).

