### 6.2 Binding

This study conducted a double-blind design to ensure that neither participants nor researchers were aware of the group assignments throughout the study. Participants, researchers, data collectors, and outcome assessors were blinded to the group allocation. Statisticians and authors were unaware of the subgroups during data analysis. Doctors, technicians and trial nurses were aware of the subgroups but were not involved in data collection or analysis.

For image quality and lesion quality scoring, we will give a mixture of CBCT, sCT, and CT images to the scorers, and they unaware of the images type.

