### 3.4 Detailed sample size calculation

The randomization process was conducted by an independent statistician who was not involved in the recruitment, treatment, or data analysis of the participants. The sample size was calculated for the primary endpoint (The mean number of intraoperative

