**Test Direction**

Alternative Hypothesis: One-Sided

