### Two-Sample T-Tests Assuming Equal Variance

#### Numeric Results for an Equal-Variance T-Test

$$\delta = \mu_1 - \mu_2$$

Hypotheses:  $H_0: \delta \leq 0$  vs.  $H_1: \delta > 0$

Target Power	Actual Power	N1	N2	N	$\delta$	$\sigma$	Alpha
0.9	0.90089	103	103	206	1	2.2	0.025

**Figure 2.** Sample size calculation process

Finally, we decided to adopt a conservative approach and include 220 participants in this study. This study will take approximately three months to complete.

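### SAP 5.5 leaves the primary test open between t-test and Mann-Whitney and omits centre, although SAP 3.4 sizes the trial on a difference in means

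*SAP*

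**What the plan says.** SAP 5.5 is the only text that assigns a test to the primary outcome: "For primary outcome, secondary outcomes and baseline comparisons between the two groups, appropriate statistical tests (parametric or non-parametric) will be applied". For continuous variables it lists the t-test and Mann-Whitney. It gives no rule for choosing, no effect measure, no confidence interval and no term for centre. Protocol section 10 lists the same two tests and makes the choice depend on the kind of data, but its sentence is introduced for baseline comparisons and does not name the primary outcome.

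SAP 3.4 is more specific. It begins "The sample size was calculated for the primary endpoint (The mean number of intraoperative" and continues with puncture times. It defines delta, set to 1, by saying that it "represents the smallest difference between the means of the two groups". It adds: "We used a 2.5% one-sided significance level with 90% efficacy for sample allocation on a 1:1 basis". Figure 2 is headed "Two-Sample T-Tests Assuming Equal Variance" and carries the setting "Alternative Hypothesis: One-Sided".

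Protocol 7.1 defines the outcome as a count of punctures over the procedure. Protocol 6.1 and SAP 3.3 stratify randomisation by centre. Both documents blind the analysis: "Statisticians and authors will be also blinded to subgroup allocation during data analysis" (SAP 3.3) and "Statisticians and authors were unaware of the subgroups during data analysis" (Protocol 6.2).

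**The concern.** The t-test compares mean punctures. Mann-Whitney asks whether a patient in one arm tends to have fewer punctures than a patient in the other. For a skewed count with many patients at the minimum, these are different questions and can have different answers. SAP 3.4 sizes the trial on the first, and SAP 5.5 permits either.

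The planning figures suggest which way the choice would go. With a mean of 2.3, an SD of 2.2 and a floor at or near one puncture, the data cannot be close to normal, and a conventional normality check would pick Mann-Whitney. The primary p-value would then not test the planned mean difference, and its power would depend on the unknown share of patients who need only one puncture. Leaving out centre also means that the analysis does not reflect the stratified randomisation.

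**Working it through.** **Inputs from the documents.** Control mean 2.3 and SD 2.2 (38 retrospective patients), delta 1, one-sided alpha 0.025, power 0.90, 103 per group raised to 110 (SAP 3.4).

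**The plan's own figure.** Exact (noncentral t) power of an equal-variance t-test with delta 1 and SD 2.2 is 0.8981 at 102 per group, 0.9009 at 103 and 0.919 at 110. Figure 2 gives 0.90089 at 103, so it is reproduced.

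**Skew.** Assume at least one puncture per procedure. Under a normal distribution the share below 1 would be Φ((1 − 2.3)/2.2) = Φ(−0.59) = 0.277, that is, 28% of patients below the minimum. In simulation with four skewed shapes, a Shapiro-Wilk test at 0.05 on the pooled, unlabelled 220 patients rejected normality in every trial.

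**Assumed shapes.** The documents give no distribution. Four control shapes were used, each with mean 2.3 and SD 2.2 and with 45%, 53%, 60% or 65% single-puncture patients. The 53% shape is 1 plus a negative binomial with mean 1.3 and variance 4.84.

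**Plain treatment effect.** GPS-Lung avoids each repeat puncture with equal probability. Repeat punctures average 2.3 − 1 = 1.3, so a difference of 1 means avoiding 1/1.3 = 77% of them, and 0.5 means 0.5/1.3 = 38%. If a fraction q of repeats remains, the GPS-Lung variance is q² × 4.84 + q(1 − q) × 1.3. At a difference of 1, q = 0.3/1.3 = 0.231, the variance is 0.49 and the SD is 0.70. The equal-SD assumption of SAP 3.4 then fails.

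Power at 110 per arm, one-sided 0.025, 20,000 trials per cell:

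| True difference | Control single-puncture share | t-test | Mann-Whitney | Tests disagree |
|---|---|---|---|---|
| 0.5 | 45% | 52.7% | 57.1% | 20.9% |
| 0.5 | 53% | 51.7% | 38.9% | 21.2% |
| 0.5 | 60% | 51.0% | 26.6% | 26.0% |
| 0.5 | 65% | 51.4% | 19.6% | 31.9% |
| 0.75 | 45% | 94.0% | 95.0% | 5.5% |
| 0.75 | 53% | 92.8% | 82.3% | 12.6% |
| 0.75 | 60% | 92.5% | 65.4% | 27.2% |
| 0.75 | 65% | 92.0% | 50.2% | 41.8% |
| 1 | 45% | 100% | 100% | 0.01% |
| 1 | 53% | 99.97% | 99.66% | 0.32% |
| 1 | 60% | 99.95% | 97.39% | 2.56% |
| 1 | 65% | 99.94% | 91.25% | 8.69% |

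The agreement at 1 depends on the bracket. A further shape with about 68% single-puncture patients gives t-test 99.9%, Mann-Whitney 82% and disagreement 18%.

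**Other mechanisms, chosen to show both directions (negative binomial control).** These are illustrations, not expectations.
- Counts capped at 3 (difference 0.55): t-test 73%, Mann-Whitney 11%.
- Difference 0.5 with both SDs 2.2: t-test 42%, Mann-Whitney 90%.
- Equal means with GPS-Lung SD 3.0: Mann-Whitney declares benefit in 32% of trials, the t-test in 3.9%.

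**No effect (identical arms).** Each test alone has an error of 2.4-2.6% for the four shapes. Reporting whichever is significant gives 3.4-3.9%.

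**The case against.** SAP 3.4 already contains a target: mean punctures, a one-sided hypothesis and a t-test. On this view all that is missing is a cross-reference from SAP 5.5. This stands in part. A reader might infer that the SAP has no target at all, and that would be wrong. But SAP 3.4 states sizing assumptions, and no sentence commits the analysis to them.

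A reader might also infer that the plan inflates the type I error. The documents do not support this. The 3.4-3.9% requires someone to run both tests and report the favourable one. No passage plans this, and the analysts are blinded. Blinding limits such a choice without excluding it, since coded arms still show both p-values. If a normality check decides, the choice is in effect settled before any result is seen, at about 2.5% error. What remains is the mismatch between sizing and analysis, which blinding does not touch.

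A third inference would be that Mann-Whitney loses power, or that 103 per group is wrong. Neither follows. The figure reproduces, and either test can be the stronger one. In the plain scenario both mostly succeed at the planned difference of 1. The wide disagreement lies below the difference the trial was sized for. That is a fair limit on the size of the problem, though a difference of 1 already requires avoiding 77% of repeat punctures, so smaller true effects are plausible.

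**Conclusion.** The concern holds as a should-fix. The primary test is not fixed, centre is left out, and the likely default for a skewed count is a test of a quantity other than the one the trial was sized on. This follows from the text and needs no simulation, except that the step to Mann-Whitney assumes a conventional normality check and at least one puncture per procedure.

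The practical size is uncertain because the documents give only a mean, an SD and a delta. With 45-65% single-puncture controls and equal-probability avoidance, the two tests lead to different conclusions in 0-9% of trials at a difference of 1, and in about 5-42% at 0.5 to 0.75. A larger single-puncture share would widen the gap. The 90% power belongs to the equal-variance t-test under normality and does not carry over to Mann-Whitney in either direction.

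**What to change.** In SAP 5.5, separate the primary outcome from the shared sentence and name one analysis: the difference in mean number of punctures (GPS-Lung minus CBCT) with a 95% CI, adjusted for centre and tested at one-sided 0.025, with a rank test as a sensitivity analysis. Add the same sentence to Protocol section 10, which at present does not mention the primary outcome. State that the 90% power was computed for an unadjusted equal-variance t-test under normality at 103 per group (0.919 at 110), and do not attribute it to the adjusted model.

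Robust standard errors (the arms may well differ in variance) and a centre-stratified rank test are options, not requirements. Another single prespecified test would also close the choice, but it would need its own target quantity and power calculation.

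The cost is wording only: centre is already recorded as the stratum, and no patients or data are added. There is a statistical price. For some skewed shapes a rank test has more power. With a difference of 1 and both SDs 2.2 (negative binomial), the centre-adjusted mean comparison with robust (HC3) standard errors has about 87% (assumed centre sizes 110/70/40), against nearly 100% for Mann-Whitney. If GPS-Lung counts are much more dispersed at an equal mean (SD 2.6 to 3.5), the one-sided error of that model is 2.9-4.5%.

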## **Study Protocol**

Study type: Prospective randomized controlled trial.

Study schedule: January 2025-May 2025 (5 months total).

Study location: Three Level 3A hospitals in China (Wuhan Union Hospital, Wuhan Union West Hospital, and Wuhan Union Jinyinhu Hospital).

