## 6 Randomization and binding

### 6.1 Randomization

Randomization was performed using a Web-based system (<https://www.randomizer.org/#randomize>) that employed computer-generated, permuted-block sequences, with stratification by center. Notably, the Web-based central randomization service ensured concealment of trial-group assignments.

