## 10 Data analysis program

The baseline comparisons between the two groups, appropriate statistical tests will be employed based on the type of data (parametric or non-parametric). Categorical variables will be analyzed using the Chi-squared test or Fisher's exact test, while continuous variables will be analyzed using the *t*-test or the Mann-Whitney U test. Paired *t*-tests will be used to compare the means of the scores for overall image quality and lesion visualization between paired groups. The weighted kappa coefficient ( $\kappa$ ) or kendall coefficient of concordance (W) or intra-class correlation coefficient (ICC) will be used to assess the agreement of the image quality of all samples and the lesions score of sCT among different readers.

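### Randomisation is stratified by centre but no between-arm test uses centre; if the three hospitals differ, the tests are conservative and some power is lost

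*SAP*

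**What the plan says.** **Randomisation.** Protocol 6.1 specifies "computer-generated, permuted-block sequences, with stratification by center", and SAP 3.3 says the same: "employing computer-generated permuted-block sequences with stratification by center". SAP 3.1 mentions only a computer-generated random sequence with 1:1 allocation, which does not contradict the explicit statements. Protocol section 3 places the trial in "Three Level 3A hospitals in China".

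**Analysis.** SAP 5.5 covers the primary outcome, the secondary outcomes and baseline in one sentence: "For primary outcome, secondary outcomes and baseline comparisons between the two groups, appropriate statistical tests (parametric or non-parametric) will be applied". It names chi-squared or Fisher's exact for categorical variables, and the t-test or Mann-Whitney for continuous ones. Protocol 10 names the same tests: "Categorical variables will be analyzed using the Chi-squared test or Fisher's exact test", with the t-test or Mann-Whitney for continuous data. Neither document mentions a centre term, a stratified test or any covariate adjustment.

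**Sample size.** SAP 3.4 states: "We used a 2.5% one-sided significance level with 90% efficacy for sample allocation on a 1:1 basis". The software output there is an unstratified equal-variance t-test. The SD of 2.2 comes from one hospital: "A total of 38 participants received CBCT-guided PLP from retrospective cohort were included from Wuhan Union Hospital".

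**The concern.** Stratified blocks keep the arms balanced within each hospital, so differences between hospitals largely cancel out of the treatment difference. An unstratified test does not use this. It estimates its error from the total variance, including the between-hospital part, so its standard error is larger than the true one. The true type I error then falls below the planned 2.5%, and power is lower than the same 220 patients could give.

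Two features of this plan make that relevant. First, the planning SD comes from a single hospital and so contains no between-hospital variation. Any such variation adds to the error term of the planned test and uses up the margin of 110 over the calculated 103 per arm. Second, the same sentence governs radiation dose, duration of surgery and complications. The paired image-score and reader-agreement analyses in SAP 5.6 do not compare the randomised arms and are not affected.

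**Working it through.** **Inputs from the documents (SAP 3.4).** One-sided alpha 0.025, power 0.90, difference 1, SD 2.2, 103 per arm calculated, 110 per arm planned, control mean 2.3.

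**Plan's own figure.** The noncentral t with 103 per arm gives power 0.90089, exactly as printed. With 110 per arm it gives 0.919.

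**Assumption.** Let R2 be the share of total variance in puncture count that lies between centres. The documents give no value, so 5, 10 and 20% are shown. To give R2 a scale, take three equal, evenly spaced centres and a within-centre SD of 2.2. The between-centre SD is then 2.2 × sqrt(R2/(1 − R2)) = 0.505 / 0.733 / 1.100. The gap between the highest and lowest centre means is 2 × sqrt(1.5) times this, or about 1.2 / 1.8 / 2.7 punctures.

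**Formulas, reading 2.2 as the within-centre SD.**
- True SE = 2.2 × sqrt(2/110) = 0.2966.
- SE used by the unstratified test = 0.2966 / sqrt(1 − R2) = 0.3044 / 0.3127 / 0.3317.
- True one-sided type I error = 1 − Φ(1.96 / sqrt(1 − R2)).
- Unadjusted power = Φ((1 − t × SE used) / 0.2966), with t = 1.971 on 218 df. At R2 = 10%: (1 − 1.971 × 0.3127) / 0.2966 = 1.293, and Φ(1.293) = 0.902.
- Adjusted power = noncentral t on 216 df = 91.9% at any R2.
- Per-arm size m at which the unadjusted test matches the adjusted one: sqrt(m/2)/2.2 = 1/0.2966 − 1.96 + 1.96/sqrt(1 − R2).

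| R2 (assumed) | Type I error, t-test | Power, unadjusted | Power, adjusted | m per arm | Extra patients, 2 × (m − 110) |
|---|---|---|---|---|---|
| 5% | 2.2% | 91.1% | 91.9% | 113.3 | about 7 |
| 10% | 1.9% | 90.2% | 91.9% | 117.0 | about 14 |
| 20% | 1.4% | 87.8% | 91.9% | 125.6 | about 31 |

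Setting unadjusted power to 90% gives R2 = 11.0%, a gap of about 1.9 punctures.

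**Reading 2.2 as the total SD.** The SE used is 0.2966 and the true SE is 0.2966 × sqrt(1 − R2). Power unadjusted versus adjusted is 92.5 vs 93.1%, 93.0 vs 94.3% and 94.1 vs 96.3%, always above 90%.

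**Checks by simulation (normal outcomes).** With centres of 74/74/72 and exact balance within centre, unadjusted power was 91.2 / 90.2 / 87.8%, against about 91.9% adjusted. Type I error was 2.3 / 2.0 / 1.4%, against about 2.5%. With unequal centres (140/50/30), unadjusted power was 90.9 / 90.2 / 87.9%, against 91.7 to 91.9% adjusted. Mann-Whitney type I error was 2.3 / 1.9 / 1.4%, against about 2.5% for van Elteren. A separate run at R2 = 10%, with permuted blocks of 4 (block size assumed), gave:
- t-test: size 0.019, power 0.898
- Mann-Whitney: size 0.018, power 0.884
- centre-adjusted linear model: size 0.024, power 0.917

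**The case against.** The strongest reply concerns the size of the effect. The outcome is a count, presumably at least 1 for a completed procedure, and the power figures use a normal model with equal SDs. With an overall control mean of 2.3, the gaps above put the lowest centre's control mean at about 1.7 / 1.4 / 0.95. A further difference of 1 puts its treated mean at about 0.7 / 0.4 / −0.05. The 20% row is therefore hard to reconcile with such a count unless the overall mean is above 2.3. A simulation with counts of at least 1 and a multiplicative effect on the excess over 1 gave almost no loss at a difference of 1: 99.98% with either analysis at the 5% gap, and 99.84 vs 99.86% at the 10% gap.

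That caution stands for the power rows, the 11% threshold and the patient equivalents, which all rest on the sponsor's own planning model. It does not remove the point. Power is near 100% in that simulation because the treated SD falls to about 0.7, which leaves little room for a loss to show. With bounded counts the test remains conservative (size about 2.1% and 1.9% at the two smaller gaps), and about 1 to 3 points of power are lost at smaller effects.

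It is also fair that the hospitals share a city and a parent name and may be similar, that the planned t-test matches the sample size calculation, and that power stays above 90% at R2 of 5 and 10%. These limit the likely loss; none is a reason to leave centre out.

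**Conclusion.** The concern holds, as an efficiency loss and not a validity error. Both documents stratify randomisation by centre, and neither uses centre in any comparison between arms. If the hospitals differ, the unstratified tests are conservative. On the planning model with 2.2 as the within-centre SD, the power loss is about 0.8, 1.7 and 4 points at R2 of 5, 10 and 20%, and power drops below the stated 90% only above about 11%. With 2.2 as the total SD, power stays above 90% throughout. If the hospitals do not differ, nothing is lost.

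The omission and the direction of its effect are certain. The size rests on an assumed R2 and on the normal, equal-SD model. No loss was calculated for radiation dose, duration or complications; the mechanism is the same, but the documents give no figures for them. The change should be made because it costs almost nothing and because adding centre after the data are seen would be a post hoc choice.

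**What to change.** In SAP 5.5, pre-specify centre (three levels) in every primary and secondary comparison between arms, and align Protocol 10:
- **Puncture count, radiation dose, duration of surgery:** a linear model with arm and centre.
- **Wherever a rank test is used:** the van Elteren test stratified by centre.
- **Complications:** the Cochran-Mantel-Haenszel test stratified by centre, in its exact version where Fisher's test would have been used.

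The cost is SAP wording, with no new data. In the linear model it uses two degrees of freedom (218 to 216); if centres do not differ, power changes by less than 0.1 percentage point (91.867% to 91.864%). The power cost of the van Elteren and exact stratified tests was not calculated. Which of the parametric and rank tests is primary is a separate choice that SAP 5.5 also leaves open, and this change does not settle it.
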